3.2 Study Population

The study cohort consists of selected hospital district areas that have INR measurements available for AF patients using warfarin. See also [Sections 3.1](#) and [3.3](#).

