3.2.1 Inclusion Criteria

Patients fulfilling the following criteria are included in the study:

- Patient has purchased warfarin (Anatomical Therapeutic Chemical classification (ATC) code B01AA03) between 01-Jan-2007 and 31-Dec-2009,
- Patient has at least one INR measurement available between 01-Jan-2007 and 31-Dec-2009, and
- Patient has a International Classification of Diseases (ICD-10 version 10) diagnosis code I48 for AF between 01-Jan-2005 and 31-Dec-2009.

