3.2.2 Exclusion Criteria

- Patients with permanent residence in Finland less than 12 months prior to index date.
- Patients with age below 18 years at index date.

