3.3 Data Source/Data Collection Process

The study timelines are presented in the picture below:

Figure 3.3-1: Study Timelines

[figure not shown]

Table 3.3-1: Study Registers

Register	Register Holder	Information obtained
National Prescription Register	Kela – The Social Insurance Institution of Finland	Drug purchases (ATC codes)
National Reimbursement Register	Kela	Reimbursement decisions 207 for chronic arrhythmias (for population characterization)
Finnish Care Register, HILMO	National Institute for Health and Welfare	Diagnoses (ICD10 codes) and date of diagnosis
National Causes of Death Register	Statistics Finland	Time of death and causes of death (ICD-10 codes)
Laboratory databases	HUSLAB + other hospital laboratories	INR measurements and other relevant laboratory values
Finnish Cancer Registry	National Institute for Health and Welfare	Cancer diagnosis (ICD-O-3 codes) and date of diagnosis
Population Register	Population Register Center	Places of domicile 12 months prior to and on index dates.
Social HILMO	National Institute for Health and Welfare	Information (dates) about institutionalization (other than hospitalization)

- Data will be requested from the registry holders ([Table 3.3-1](#)) based on the study protocol.
- Data permits will be requested from each registry holder based on the study protocol and ethical approval.
- Approval of Ethical Review Board of Hospital District of Helsinki and Uusimaa (HUS) will be requested to cover the nationwide study.
- This is a fully register-based study and patients will not be contacted in any phase of the study.
- Warfarin exposure will be defined by Kela, who then will convert the patient IDs to study IDs (SIDs). Kela will then send the IDs and the SIDs to other register holders: Statistics Finland, National Institute for Health and Welfare, Statistics Finland, Population Register Center, and central hospital laboratories included in the study.
- EPID Research will receive unidentifiable data including SIDs only. All patient data handled by the researchers are then anonymous which ensures full data protection of the patients.

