3.4 Definitions of Study Variables

3.4.1 Outcomes/Endpoint Variables

The studied primary outcomes/endpoint variables of interest are defined through ICD-10 diagnosis codes (hospitalizations and deaths) or ICD-O-3 codes (cancers). See [Appendix 1](#) and [2](#) for more detail.

The time to event for each primary outcome will be calculated as the time from the index date to the time of the diagnosis of the outcome when such an event occurs during the follow-up.

Index date is defined as the date of first purchase of warfarin after 01-Jan-2007. Follow-up of the patients starts on the index date, and ends on 31-Dec-2011, at time of death or at time of emigration whichever occurs first. Treatment and comorbidity history is gathered from the period 01-Jan-2005 to 31-Dec-2006.

Primary outcomes:

- Stroke
- Other systemic thromboembolic events excluding stroke
- Myocardial infarction
- Bleeding events
- Mortality all-cause
- Mortality (stroke)
- Mortality (myocardial infarction)
- Mortality (systemic thromboembolic events excluding stroke)
- Mortality (bleeding events)

The studied secondary outcomes/endpoint variables of interest are anemia and renal impairment.

Time to anemia is defined as the time from index date to time of first decrement of 20 g/L in haemoglobin or time when haemoglobin is under the reference value.

Time to renal impairment is defined as the time from index date to time when creatinine is under the reference value.

Secondary outcomes

- Anemia
- Renal impairment

In the statistical analysis follow-up for each time to event outcome continues until the time of the event, death, emigration or 31-Dec-2011 whichever comes first.

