3.4.2 Exposure/Independent Variables of Interest

- Performance of warfarin therapy
 - INR values under 2.0, 2.0-3.0, and over 3.0
 - time to reach the target INR 2.0–3.0
 - TTR, percentage of time during which the interpolated INR values lie between 2.0 and 3.0¹³
- Exposure to warfarin (ATC B01AA03)
 - new vs. prevalent users (< vs. > 90 days)
 - time since discontinuation
- I48 diagnosis
 - yes/no
 - time from the diagnosis
- Place of domicile 12 months prior to and on the index date
 - if not in Finland, excluded
- Use of antiarrhythmic drugs:
 - yes/no
 - ◆ Group C01B: antiarrhythmic drugs, classes I and III (see [Appendix 3, Table 1](#) for details)
 - ◆ Group C07: beta blockers / class II antiarrhythmics (see [Appendix 3, Table 2](#) for details)
 - ◆ C08DB01: diltiazem (class IV antiarrhythmic)
 - ◆ C08DA01: verapamil (class IV antiarrhythmic)
- Use of other anticoagulant or reimbursed antithrombotic therapy:
 - heparins (B01AB01, B01AB51), clopidogrel (B01AC04), dipyridamole (B01AC07), ticlopidine (B01AC05), prasugrel (B01AC22)

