5 STUDY LIMITATIONS/STRENGTHS

Finland has a well-developed population register system with tens of years of longitudinal follow-up data. The persons are identified in the registers with a unique personal identification number enabling linkage between different registers. These data has not been collected for study purposes, which may affect the quality of the data. However, these registers have been considered reliable for scientific research purposes.

Only those citizens that have been living in Finland for 12 months prior to index date will be included in the study.

No exact prescribed dosing information is available. Dosing is assumed based on the information of purchases and package sizes with defined daily doses (DDDs).

Coverage of the Prescription Register containing reimbursement information of all permanent residents of Finland is about 97%. Missing data includes relatively inexpensive packages which are not reimbursed. Fully reliable information on eg, acetylsalicylic acid use is then not available.

Medications used during hospitalizations are not available. However, based on the hospital care register the hospitalization periods can be taken into account to define gaps in the drug treatment periods.

No nationwide database about laboratory measurements is available. The laboratory data is then collected from separate local central laboratories. All laboratory values for particular patients may then not be available. Also changes in places of domicile may affect the follow-up of the patients. On the other hand, previous published surveys on the subject have not included INR follow-up to this extend.

To avoid selection bias, the cohort time (years 2007 to 2009) was chosen to avoid complication of patients switching from warfarin to newer anticoagulant medications eg, dabigatran.

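### No criterion requires living in a participating hospital district, and residence is not obtained after index, so time outside the laboratory catchment cannot be removed and emigration censoring has no listed data source

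*Protocol*

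**What the plan says.** Protocol section 3.2 describes the cohort geographically: "The study cohort consists of selected hospital district areas that have INR measurements available for AF patients using warfarin". The criteria that build it do not. Section 3.2.1 asks for a warfarin purchase, an I48 diagnosis and the following: "Patient has at least one INR measurement available between 01-Jan-2007 and 31-Dec-2009". Section 3.2.2 excludes minors and "Patients with permanent residence in Finland less than 12 months prior to index date". Section 3.4.2 lists domicile 12 months before and on the index date, and its one stated use is "if not in Finland, excluded".

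Table 3.3-1 takes diagnoses and deaths from registers named without any district limit, and INR from HUSLAB and other hospital laboratories. The Population Register row reads "Places of domicile 12 months prior to and on index dates". No row gives residence after index or a date of emigration.

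Section 3.4.1 states: "Follow-up of the patients starts on the index date, and ends on 31-Dec-2011, at time of death or at time of emigration". The Synopsis and section 3.1 say the same, and section 3.4.1 repeats emigration in its closing rule for the time-to-event analyses. Section 4.1 sets the daily INR to the previous measurement, or to a linear interpolation that reverts to the previous measurement when the gap exceeds 60 days. No upper limit on that carry-forward is stated. Section 5 says that not all laboratory values may be available and adds: "Also changes in places of domicile may affect the follow-up of the patients".

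**The concern.** Exposure and outcome are captured over different territories. Outcomes follow the patient through the registers, while INR is seen only where a participating laboratory measured it. A design of this kind needs a rule that keeps person-time inside the area where exposure can be observed, and the protocol has none at entry or during follow-up.

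Three consequences follow. First, patients whose routine INRs are measured elsewhere, and patients who move away, add events and person-time under an INR category that may no longer describe them. The primary hazard ratios are then estimated on misclassified exposure. Second, emigrants remain in the denominator until 31-Dec-2011 with no events recorded, which lowers incidence rates. Third, one INR anywhere in a three-year window is enough, and it may fall after the index date. Entry of an out-of-area patient can therefore depend on a later hospital contact inside the area.

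**Working it through.** **1. The planned population (section 4.2).** 3,000,000 × 0.016 × 0.67 = 32,160 (stated: 32 000). At 3 years each this is 96,480 person-years (stated: 96 000). 96,000 × 21.7% / 63.6% / 14.7% = 20,832 / 61,056 / 14,112 person-years (stated: 21000 / 61000 / 14000). The figures reproduce. Their base is the population of the participating areas, a restriction that sections 3.2.1 and 3.2.2 do not impose.

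**2. Rules against data.**

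| Needed | Supplied |
|---|---|
| Cohort of selected districts (3.1, 3.2) | Residence tested for Finland only (3.2.2, 3.4.2) |
| Follow-up to 31-Dec-2011 (3.1, 3.4.1) | Domicile ends at the index date (Table 3.3-1) |
| Censoring at emigration (Synopsis, 3.1, 3.4.1) | No emigration date in any row of Table 3.3-1 |
| Current daily INR (4.1) | Participating laboratories only; previous value carried forward, no stated limit |

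**3. Following two patients through the rules.** A patient who moves to a non-participating district keeps the last INR category, because section 4.1 applies the previous measurement. The stopping rule in section 4.1.2 (Objective 3) needs a gap in both warfarin exposure and INR, so a mover who still buys warfarin counts as treated. A patient who always lived outside the area and has one INR inside it has no INR category before that date and the same category from then on.

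**4. Size, by illustration.** Let m be the share of person-time whose INR category is unrelated to the true one. The protocol gives no value for m. Assume a true relative risk (RR) of 1.20 for INR below 2.0, with the over-3.0 group at the reference rate.

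Average relative rate: 0.217 × 1.20 + 0.636 + 0.147 = 1.0434.

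Observed RR = [(1 − m) × 1.20 + m × 1.0434] / [(1 − m) + m × 1.0434].

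- m = 0.05: 1.19217 / 1.00217 = 1.19
- m = 0.10: 1.18434 / 1.00434 = 1.18

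For power, the protocol states neither alpha nor formula. With two-sided 0.05 assumed, the following form comes within 1 point of every cell of Table 4.2-1. It is a pooled two-proportion test with group 1 at the listed rate, the reference at rate/RR and person-years grouped in two-year units. It was found by trial and is not stated in the protocol. For 1.5 per 100 person-years and RR 1.20:

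- n1 = 21,000/2 = 10,500 and n2 = 61,000/2 = 30,500
- p1 = 0.030 and p2 = 0.030/1.20 = 0.025
- SE under the null 0.00181, SE under the alternative 0.00189
- z = (0.005 − 1.96 × 0.00181)/0.00189 ≈ 0.77, power 77.9% (Table 4.2-1: 78.6%)

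With the observed RR in place of 1.20:

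| m | Observed RR (true 1.20) | Power | Observed RR (true 1.50) |
|---|---|---|---|
| 0 | 1.20 | 77.9% | 1.50 |
| 5% | 1.19 | 74.1% | 1.47 |
| 10% | 1.18 | 70.0% | 1.45 |
| 20% | 1.16 | 60.7% | 1.39 |
| 30% | 1.14 | 50.6% | 1.34 |

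**5. How large might m be from moves alone?** Assume a constant rate r of moving out of the area. The share of a 3-year follow-up spent after a move is 1 − (1 − e^(−3r))/(3r). For r = 0.5-2% per year, also an assumption, this is 0.7-2.9%, or about 700-2,800 of 96,000 person-years. On those rates movers alone stay below the 5% row.

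**The case against.** The strongest reply is that the harm is limited and partly acknowledged. Section 5 discloses local laboratories, incomplete values and changes of domicile. Section 3.4.3 lists hospital district as a covariate, and section 4.2 repeats the power calculation at 80% of the population to allow for missing INR. All true, but none of these is a rule. The 80% calculation treats missing INR as fewer patients, not as misclassified time. Section 5 does not mention that emigration dates are absent from the data list.

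A reader might infer something stronger: that an out-of-area patient admitted with a stroke or bleed enters on the INR taken at that admission, so that the acute value is tied directly to the event. Section 4.1 does not support this. A patient with no earlier INR has no previous value and nothing to interpolate, so the time before the event is unclassified, and follow-up for that outcome ends at the event. What stands is narrower. Handling of an INR on the event day is not stated, and the acute value can be carried forward to later outcomes such as death. Nor do the documents give any basis for saying what share of strokes would come from such entrants.

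Two further limits stand. The geographic scope of Kela's identification of warfarin purchasers is not stated, so nationwide identification is an inference. And emigration censoring is impossible only on the fields listed, since the Population Register is already a source.

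The SAP, which is not at hand, may cap the carry-forward. It could not supply a missing field: section 3.3 has data requested on the basis of the protocol.

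**Conclusion.** The point holds as a gap between the protocol's rules and its data. The cohort described and sized by district is not restricted to those districts. Residence is unknown after index, and one of the stated ends of follow-up has no listed source. The effect is exposure misclassification among movers and out-of-area patients, unrecorded loss of emigrants, and entry that can depend on a later hospital contact.

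The size is not known. At 5-10% of person-time with an unrelated INR category, a true RR of 1.20 is seen as about 1.19-1.18 and power drops from about 78% to 74-70% at 1.5 events per 100 person-years. This rests on the assumed shares, on misclassification unrelated to outcome and on a power formula inferred from the table. An old INR may still carry some information, which would make the loss smaller. Entry linked to hospital contact is not modelled and need not act in the same direction. The documents support a correctable design weakness, not a claim that the primary comparison is dominated by referral bias.

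**What to change.** - Section 3.2.1: add domicile in a participating hospital district on the index date. Leave the 12-month residence rule at the level of Finland. Requiring district domicile 12 months earlier as well would drop people who moved in before index and whose later INRs are captured.
- Table 3.3-1, Population Register row: request dated domicile and emigration from 12 months before index to 31-Dec-2011.
- Sections 3.1 and 3.4.1: for the INR and TTR analyses, also end follow-up at the date of moving out of the participating districts.

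The cost is one criterion, one wider field from a register already being linked, and one censoring rule. Table 3.1-1 places data permits after protocol approval, so the field can go into the same requests. Some patients and person-time are lost. The change does not help residents whose INRs are missing for other reasons.

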3.4 Definitions of Study Variables

3.4.1 Outcomes/Endpoint Variables

The studied primary outcomes/endpoint variables of interest are defined through ICD-10 diagnosis codes (hospitalizations and deaths) or ICD-O-3 codes (cancers). See [Appendix 1](#) and [2](#) for more detail.

The time to event for each primary outcome will be calculated as the time from the index date to the time of the diagnosis of the outcome when such an event occurs during the follow-up.

Index date is defined as the date of first purchase of warfarin after 01-Jan-2007. Follow-up of the patients starts on the index date, and ends on 31-Dec-2011, at time of death or at time of emigration whichever occurs first. Treatment and comorbidity history is gathered from the period 01-Jan-2005 to 31-Dec-2006.

Primary outcomes:

- Stroke
- Other systemic thromboembolic events excluding stroke
- Myocardial infarction
- Bleeding events
- Mortality all-cause
- Mortality (stroke)
- Mortality (myocardial infarction)
- Mortality (systemic thromboembolic events excluding stroke)
- Mortality (bleeding events)

The studied secondary outcomes/endpoint variables of interest are anemia and renal impairment.

Time to anemia is defined as the time from index date to time of first decrement of 20 g/L in haemoglobin or time when haemoglobin is under the reference value.

Time to renal impairment is defined as the time from index date to time when creatinine is under the reference value.

Secondary outcomes

- Anemia
- Renal impairment

In the statistical analysis follow-up for each time to event outcome continues until the time of the event, death, emigration or 31-Dec-2011 whichever comes first.

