2 OBJECTIVES

2.1 Primary Objectives

- 1) To investigate and compare risk of stroke, systemic thromboembolic events, and myocardial infarction among AF patients in relation to INR levels: under 2.0, 2.0-3.0, and over 3.0.
- 2) To investigate and compare risk of bleeding events among AF patients in relation to INR levels: under 2.0, 2.0-3.0, and over 3.0.
- 3) To investigate and compare mortality risk among AF patients in relation to INR levels: under 2.0, 2.0-3.0, and over 3.0.

The primary objectives are evaluated separately for prevalent users of warfarin and for new users of warfarin.

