4 STATISTICAL ANALYSIS

4.1 Statistical Analysis Methods

Data management, tabulations, graphics, and statistical modeling in carried out with R language (<http://www.r-project.org>). R language is described more detailed in report "R: Regulatory

Compliance and Validation Issues: A Guidance Document for the Use of R in Regulated Clinical Trial Environments" (<http://www.r-project.org/doc/R-FDA.pdf>)

A separate statistical analysis plan (SAP) including detailed statistical analysis and outputs will be produced by EPID research prior to performing any analysis.

Study population: The study population will be described at baseline (start of follow-up) using by previous drug exposure and other covariates.

Study outcomes: All study outcomes will be summarized by drug exposure and other covariates.

Drug exposure: Drug exposure starts at date of purchase. The length of the exposure period is calculated as $DDD/dose \times 1.5$, where DDD (daily defined dose) is the total amount purchased and “dose” is the amount used daily (one for an average person). For the first purchase “dose=1” and for other purchases the “dose” is calculated from previous use by dividing the previous DDD with the time between the present and the previous purchase.

The impact of the multiplier 1.5 in the construction of drug exposure will be evaluated for the primary objectives in sensitivity analyses by using multiplier values 1.25, 1.5 and 2. We will also perform a sensitivity analysis for the primary objectives by including only those patients with at least two purchases of prescriptions within a clinically meaningful timeframe of 3 months after the index date.

INR levels: Daily INR levels are calculated:

- 1) As the previous recorded INR measurement
- 2) By linear interpolation between two consecutive INR measurements. If the gap between the measurements is more than 60 days the previous measurement is applied.

Daily INR estimates are categorized into levels: under 2.0, 2.0-3.0, over 3.0. In addition when appropriate a finer categorization is used: under 1.5, 1.5-2.0, 2.0-3.0, 3.0-4.0, 4.0-5.0, 5.0-9.0, and over 9.0. This finer categorization will be used only in the analysis of the primary objectives.

Time in therapeutic range (TTR): The INR target value for AF patients is 2.0-3.0. In addition for stroke, systemic thromboembolic events, and myocardial infarction INR target above 2.0 is considered and for bleeding events INR target under 3.0 is considered.

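### With no lag in the daily INR, a death can be charged to an INR measured after the fatal illness began, which can inflate the mortality hazard ratio for INR under 2.0

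*Protocol*

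**What the plan says.** Primary objective 3 (Protocol section 2.1) is "To investigate and compare mortality risk among AF patients in relation to INR levels: under 2.0, 2.0-3.0, and over 3.0". Five of the nine primary outcomes in section 3.4.1 are deaths: all-cause, and deaths from stroke, myocardial infarction, other systemic thromboembolism and bleeding.

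- **Event time.** Section 3.4.1: "The time to event for each primary outcome will be calculated as the time from the index date to the time of the diagnosis". The same section adds that "follow-up for each time to event outcome continues until the time of the event, death, emigration or 31-Dec-2011 whichever comes first". Table 3.3-1 takes the time and causes of death from the National Causes of Death Register.
- **Daily INR.** Section 4.1 gives two methods: (1) "As the previous recorded INR measurement"; (2) "By linear interpolation between two consecutive INR measurements", falling back on the previous value when the gap exceeds 60 days. Neither has a lag.
- **INR source.** Table 3.3-1: "HUSLAB + other hospital laboratories". Values taken during a hospital stay are not excluded.
- **Model.** Section 4.1.1 compares the INR levels in a Cox model, with 2.0-3.0 as reference.

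**The concern.** A patient may have a high or in-range INR when a fatal bleed or stroke begins. If warfarin is then withheld or reversed and a new INR under 2.0 is recorded before death, that low value becomes the previous recorded measurement. The bleed or stroke itself is charged to the INR before it, but the death, if dated at death, is charged to INR under 2.0. The same can happen in a terminal stay for any cause.

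This differs from the look-ahead problem of interpolation. The misleading INR precedes the death, so method 1 is affected even though it uses no later value. Method 2 offers no escape, since after a patient's last measurement there is nothing to interpolate towards.

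At stake is the meaning of the under-2.0 hazard ratio in primary objective 3. Part of it could reflect the response to the fatal illness rather than the effect of low anticoagulation. Fatal and non-fatal bleeding could also point to different INR categories in the same report.

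**Working it through.** **1. Does anything in the protocol block it?**

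- Section 3.4.3 uses hospitalisation dates to define discontinuation of warfarin, and section 5 says they can be used to define treatment gaps. Neither ties them to INR assignment.
- The only stated end-of-treatment rule (section 4.1.2, objective 3) needs a gap of more than 2 months, and section 4.1 stretches exposure periods by a factor of 1.5. A death within days or weeks of withholding would normally still count as on treatment.
- The sensitivity analyses cover the multiplier and the two-purchase rule (section 4.1) and history of AF (section 4.1.1). None varies the timing of INR.

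**2. The protocol's own figures.** Section 4.2 takes 96 000 person-years split 21.7% / 63.6% / 14.7%, which gives 20 832 / 61 056 / 14 112, rounded there to 21 000 / 61 000 / 14 000. I compared two rates as proportions per person-year (unpooled variance, two-sided 5% assumed, stated rate taken as the overall rate). The results for N = 32 000 are:

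| Relative risk, rate per 100 patient-years | Table 4.2-1 | Recomputed |
|---|---|---|
| 1.20, 1.5 | 78.6% | 80.0% |
| 1.15, 3.0 | 86.1% | 86.5% |
| 1.10, 6.0 | 86.2% | 85.2% |

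All 36 cells agree within 2 points, so the person-years and the 10-20% detectable differences are a sound yardstick.

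**3. Size of the bias.** Assume the same true death rate in all three categories (true HR 1.00). Let f be the share of deaths at INR 2.0-3.0 and over 3.0 that is recorded under 2.0, with negligible person-time moved. In thousands of person-years, 61 + 14 = 75, so

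observed HR (under 2.0 vs 2.0-3.0) = [(21 + 75f) / 21] / (1 - f).

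The death rate cancels. The documents give no value for f, so it is shown as a range:

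| f | (21 + 75f)/21 | 1 - f | Observed HR |
|---|---|---|---|
| 0 | 1.000 | 1.00 | 1.00 |
| 1% | 1.036 | 0.99 | 1.05 |
| 2% | 1.071 | 0.98 | 1.09 |
| 3% | 1.107 | 0.97 | 1.14 |
| 5% | 1.179 | 0.95 | 1.24 |
| 10% | 1.357 | 0.90 | 1.51 |

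Worked case at f = 3% and 3 deaths per 100 person-years: 630 / 1830 / 420 deaths. Moved: 0.03 × (1830 + 420) = 67.5. Rates become 697.5/21 000 = 3.32 and 1775.1/61 000 = 2.91 per 100, ratio 1.14.

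**4. How small an f matters.** Solving for f gives f = 21(HR - 1) / (75 + 21·HR).

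- HR 1.10: 2.1/98.1 = 2.1%
- HR 1.15: 3.15/99.15 = 3.2%
- HR 1.20: 4.2/100.2 = 4.2%

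**5. Chance of a false finding at f = 3%.** At 3 per 100, ln 1.141 = 0.132, the standard error is √(1/697.5 + 1/1775.1) = 0.0447, and z = 2.96. The probability of exceeding 1.96 is about 84%. At 6 per 100 it is about 99%.

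**The case against.** The strongest reply is that the protocol never says a death takes the INR of the day of death. Section 3.4.1 speaks of the time of the diagnosis, which for a fatal stroke, infarction, embolism or bleed could mean the diagnosis of that event. On that reading the cause-specific outcomes are largely safe. This stands as a point about ambiguity, but it does not help all-cause mortality, where only the date of death fits.

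Second, section 4.1 leaves detail to a separate SAP, which could add a lag. But the daily INR rule is fixed in the protocol, and an SAP that followed it as written would carry the problem over.

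Third, hospital periods may be treated as treatment gaps, which could shrink the bias. The wording is permissive and not linked to INR, so this is a possibility and not a safeguard.

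Fourth, section 4.1.1 also analyses TTR categories, and section 4.1 defines TTR over the previous 1 to 10 months or the previous 5 and 10 measurements. The longer windows are much less affected by a few final values. That stands.

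Fifth, f is an assumption, and the calculation lets deaths move only into INR under 2.0. Movement in the other direction would offset some of the effect. That also stands.

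A reader might infer more: that fatal events at high or in-range INR are systematically counted under 2.0, or that bleeding mortality will appear highest there. The documents do not support this. Only deaths with a new INR under 2.0 recorded between onset and death move, and the rest keep their earlier category. The documents give neither how often this happens nor bleeding-death rates by INR level.

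**Conclusion.** The concern holds in a limited form. As written, sections 3.4.1 and 4.1 allow a death to be charged to an INR that follows, and results from, the fatal illness. This applies to all-cause mortality, and to cause-specific mortality if it is dated at death. The expected direction is an inflated hazard ratio for INR under 2.0.

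The actual size is unknown. With equal true rates, one-way movement and unchanged person-time, a share of about 2% to 4% of deaths is enough to produce a false hazard ratio of 1.10 to 1.20, the range the study says it can detect. The INR-level mortality analyses carry the risk. TTR over the longer windows is less exposed.

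**What to change.** Amend sections 3.4.1 and 4.1 as follows.

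1. **Cause-specific deaths.** Date fatal stroke, myocardial infarction, embolic and bleeding events at the diagnosis or admission of that event, and take the last INR before that date. Where there is no such hospital episode, the date of death remains.
2. **All-cause mortality.** Use one INR rule for all patients and all person-time. Either hold INR at its last pre-admission value throughout every hospital stay, whether or not it ends in death, or use a fixed, stated lag. Freezing INR only in stays that end in death would assign exposure by the future outcome and would treat cases differently from their risk sets.
3. **Sensitivity analysis.** Report the unlagged day-of-death version alongside.

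The cost is wording and one derived variable, built on the hospitalisation dates in section 3.4.3. Confirm that admission and discharge dates are part of the HILMO request, because Table 3.3-1 lists only diagnoses and their dates. The downside is small: genuine INR changes during a hospital stay or within the lag are ignored. A lag also helps only where it is longer than the time from onset to death.
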